8.7 Seizure/Epilepsy History

Epilepsy classification and history of seizures by type will be summarized by OLE treatment group for OLE-SE population and will be included in a by-subject listing.

Duration of epilepsy diagnosis (years) will be estimated using year of diagnosis as collected on the CRF.

9 EFFICACY ENDPOINTS

During OLE subjects will records number of seizures by seizure type in the daily dairy. Data from OLE seizure diary will be used to assess percent reduction in seizure frequency over time in subjects with longer exposure to YKP3089.

Percent reduction in seizure frequency will be calculated over the entire OLE phase (overall) and by both 6-month intervals after the start of OLE and cumulative intervals with 6-month increment.

Definitions and Derivations:

- The baseline seizure frequency per 28-day will be based on the baseline seizure diary collected prior to the first dose date in the DB period. This will be calculated by counting the number of seizures over the baseline period, dividing by the number of days in the baseline period with nonmissing seizure data, and then multiplying by 28.
- Overall seizure frequency per 28-day during OLE phase will be calculated by counting the number of seizures over the entire OLE phase, dividing by the number of days in the OLE phase with non-missing seizure data, and then multiplying by 28.
- Seizure frequency per 28-day by 6-month intervals during OLE phase will be calculated by counting the number of seizures reported during the respective 6-month interval, dividing by the number of days in the respective 6-month intervals with non-missing seizure data, and then multiplying by 28.

The following 6-months intervals will be defined for OLE seizure frequency per 28-day derivations:

6-Months Interval	OLE Phase Diary Study Days
1 – 6 Months	1 to 182
7 – 12 Months	183 to 365
13 – 18 Months	366 to 547
19 – 24 Months	548 to 730
25 – 30 Months	731 to 912
31 – 36 Months	913 to 1095

37 – 42 Months	1096 to 1277
43 – 48 Months	1278 to 1460
49 – 54 Months	1461 to 1642
55 – 60 Months	1643 to 1825
61 – 66 Months	1826 to 2007
67 – 72 Months	2008 to 2190
73 – 78 Months	2191 to 2372
79 – 84 months	2373 to 2555
85 – 90 months	2556 to 2737
91 – 96 months	2738 to 2920
97 – 102 months	2921 to 3102
103 – 108 months	3103 to 3285
109 – 114 months	3286 to 3467
115 – 120 months	3468 to 3650
>120 Months	>3650 (to last study day diary in OLE)

Study day 1 = day of the first dose in OLE phase.

 Seizure frequency per 28-day by cumulative intervals with 6-month increment during OLE phase will be calculated by counting the number of seizures reported during the respective cumulative intervals, dividing by the number of days in the respective cumulative intervals with nonmissing seizure data, and then multiplying by 28.

The following cumulative intervals will be defined:

6-Months Interval	OLE Phase Diary Study Days
1 – 6 Months	1 to 182
1 – 12 Months	1 to 365
1 – 18 Months	1 to 547
1 – 24 Months	1 to 730
1 – 30 Months	1 to 912
1 – 36 Months	1 to 1095
1 – 42 Months	1 to 1277
1 – 48 Months	1 to 1460
1 – 54 Months	1 to 1642
1 – 60 Months	1 to 1825
1 – 66 Months	1 to 2007
1 – 72 Months	1 to 2190
1 – 78 Months	1 to 2372
1 – 84 Months	1 to 2555
1 – 90 Months	1 to 2737
1 – 96 Months	1 to 2920
1 – 102 Months	1 to 3102
1 – 108 Months	1 to 3285
1 – 114 Months	1 to 3467
1 – 120 Months	1 to 3650

Study day 1 = day of the first dose in OLE phase.

For both seizure frequency per 28-day by 6-month intervals during OLE phase and seizure frequency per 28-day by cumulative intervals with 6-month increment during OLE phase, percent change from baseline will be computed as [(OLE reporting interval seizure frequency per 28-day - baseline seizure frequency per 28-day) / baseline seizure frequency per 28-day] x 100.

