In the Phase 2a study, 113 subjects received YKP3089 and 109 received placebo. Comparison of the primary efficacy endpoint, median percent reduction in partial seizure frequency, demonstrated a highly statistically significant effect in favor of the YKP3089 group, 55% vs 21%, $p < 0.0001$. Initial efficacy was observed at doses of 50-100mg/day and maintained throughout the 12 week study. Review of the safety data indicated that 4% of subjects in the active and 4% of subjects in the placebo-group dropped out because of adverse events. Two-thirds of subjects completed the study at the target dose of 200mg/day. The most common central nervous system adverse events in the YKP3089 group were somnolence, dizziness, fatigue, and gait disorder.

Two suspected unexpected serious adverse reaction (SUSAR) occurred in YKP3089 treated subjects: an early manifestation of a drug hypersensitivity reaction characterized by flushed

erythema of palms and soles with mild itching of ears and a status epilepticus during tapering. During the open-label extension, 2 notable serious adverse events occurred in YKP3089 treated subjects: one case of sudden unexpected death in epilepsy (SUDEP) and one case of suicide. They were considered remotely related or unrelated to study drug.

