8 STUDY PATIENTS

8.1 Analysis Population

Open-Label Extension Safety Evaluable Population (OLE-SE): All subjects treated in DB who continued into OLE phase and took at least one dose of open-label study medication. All OLE safety analysesdescribed in this SAP will be performed using OLE-SE.

Open-Label Extension Efficacy Analysis Population(OLE-EA): All subjects who entered in OLE phase, took at least one dose of open-label medication and have any seizure data recorded in OLE seizure diary. All OLE efficacy analyses descried in this SAP will be performed by OLE-EA

Double-Blind and Open-Label Extension Safety Evaluable Population: All subjects who received at least one dose of study medication in either DB period only (ie, subjects treated in DB who did not continue in OLE phase) or in both DB and OLE (ie, subjects included in OLE-SE population). This analysis population will be considered when reporting protocol deviations.

OLE analysis summary results will be presented by the following treatment groups:

- All YKP3089 OLE
- YKP3089 100mg DB to YKP3089 OLE
- YKP3089 200mg DB to YKP3089 OLE
- YKP3089 400mg DB to YKP3089 OLE

Placebo DB to YKP3089 OLE,

where YKP3089 100mg, 200mg, 400mg DB, and Placebo DB represent the randomized treatment group in double blind period and YKP3089 OLE represents the treatment given during OLE.

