11.2 Efficacy Analysis

11.2.1 Seizure Diary - Percent Change During OLE

The endpoint based on seizure diary is defined as: percent change (reduction) from the pretreatment baseline phase in seizure frequency (average monthly seizure rate per 28 days) of all simple partial motor, complex partial, or secondarily generalized seizures compared with the seizure frequency over the entire OLE phase (overall) and by both 6-month intervals after the start of OLE and cumulative intervals. Endpoint definitions are included in Section 9.

Summary results (mean, SD, median, minimum, and maximum) will be presented by OLE treatment groups for OLE-EA population. Subjects in OLE-EA population with no seizure diary data for the reporting OLE interval will be counted under "missing" category.

There will be no hypothesis testing for efficacy endpoints during OLE. Results will be reported descriptively by OLE treatment groups.

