11.3.2 Analysis of Clinical Laboratory parameters

Laboratory results during open-label extension will be summarized by OLE treatment groups. For these summary tables, results will be reported using visit windows as defined in Appendix 14.2. Shift tables from baseline to each post-baseline OLE visit will be prepared for hematology and chemistry laboratory assessments based on the categories of Low, Normal, and High (for numerical results) or Abnormal and Normal (for categorical results). Baseline measurement is defined as the last available measurement prior to dosing in double-blind.

Laboratory results during OLE will be listed by subject.

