11.3.3 Analysis of Electrocardiograms

All ECG results will be listed on a by-subject basis. ECG parameters consist of heart rate (bpm), PR interval (msec), RR interval (msec), QRS-complex (msec), uncorrected QT interval (msec), and QTcF interval (msec). Individual ECG values (parameters) will be listed by subject and visit. Baseline measurement is defined as the last available measurement prior to dosing in double-blind period.

For summary tables, the following rules will be applied to derive a single value corresponding for this visit:

- For all numerical values, the average of the 3 measurements will be computed
- For qualitative values (normal / abnormal):

SAP-OLE Version Final_15May2021 Page 30 of 43

- If 2 or more results are "abnormal", visit 3 derived results will be "abnormal" (this rule applies for subjects with 3 or 2 measurements)
- Otherwise, visit 3 derived results will be "normal".

For subjects with only one measurement collected at Visit 1 (DB baseline),

the collected value will be used as baseline value for summary results.

For the OLE-SE analysis population the following summary tables will be generated for the ECG data:

- Summary statistics (n, mean, standard deviation, median, minimum, and maximum) of the baseline value, the value at each scheduled postbaseline evaluation, and the corresponding change from baseline for each continuous ECG parameter,
- Count and percentage of subjects with QTcF absolute value > 450 msec, >480 msec, >500 msec, <360 msec, <340 msec, <320 msec, and <300 msec at each scheduled post-baseline evaluation,
- Count and percentage of subjects with a mean change from baseline in QTcF intervals >30 msec, >60 msec >90 msec, <30 msec, <60 msec, and <90 msec at each scheduled post-baseline evaluation,
- Count and percentage of subjects with absolute heart rate > 100 bpm at each scheduled post-baseline evaluation,
- Count and percentage of subjects with heart rate change from baseline >10 bpm, >20 bpm, and >30 bpm at each scheduled post-baseline evaluation,

For these summary tables, results will be reported using visit windows as defined in Appendix 14.1.

ECG results during OLE will be listed by subject.

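### For former placebo subjects the OLE SAP measures change only from the pre-double-blind baseline, 18 weeks before their first YKP3089 dose; adding a pre-YKP3089 reference for that group is a cheap improvement

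*SAP*

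**What the plan says.** SAP 9 defines one seizure baseline for all OLE groups, "based on the baseline seizure diary collected prior to the first dose date in the DB period". For the 6-month and cumulative intervals, "percent change from baseline will be computed as" the interval rate minus that baseline, divided by that baseline. SAP 11.2.1 names the same pretreatment reference for the overall OLE rate and for all intervals. SAP 9 gives the purpose as assessing "percent reduction in seizure frequency over time in subjects with longer exposure to YKP3089".

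The safety measures follow the same rule. For laboratory data (SAP 11.3.2), "Baseline measurement is defined as the last available measurement prior to dosing in double-blind". For ECG (SAP 11.3.3), "Baseline measurement is defined as the last available measurement prior to dosing in double-blind period", and SAP 11.3.4 repeats this for vital signs.

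SAP 8.1 reports former placebo subjects as "Placebo DB to YKP3089 OLE" and also within the pooled All YKP3089 OLE column. Under Protocol 6.1.4.1 and Table 5 they first take YKP3089 in Week 1 of the conversion period, which begins at Visit 9 (Day 127).

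Adverse events are handled differently. SAP 10.1 judges treatment emergence from the start of OLE medication, in every group.

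**The concern.** In the three groups randomised to YKP3089, the pre-double-blind baseline is the last state before the drug. In the former placebo group it is not: 18 weeks on placebo lie between that baseline and the first YKP3089 dose. Improvement in those weeks is carried into a figure whose stated purpose concerns exposure to YKP3089.

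Some improvement is to be expected without any drug. Inclusion criterion 6 (Protocol 7.3) admits subjects on the same diary that supplies the baseline: at least 8 seizures in 8 weeks and at least 3 in each 4-week half. Rates selected in this way tend to fall afterwards.

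The SAP plans no double-blind seizure rate beside the OLE rates, and no change from a value before the first YKP3089 dose. A reader of this group's row therefore cannot tell how much of the reduction was there before treatment started. In the same way, a laboratory shift or QTcF change that arose on placebo would be tabulated as a change during OLE.

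**Working it through.** **Interval.** The plan's own figure is 18 weeks, 6 of titration plus 12 of maintenance. From the visit schedule, (127 − 1)/7 = 18.0 weeks, which agrees.

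**Re-basing.** Let B be the pre-double-blind rate, P = (1 − p)B the double-blind placebo rate and O = (1 − r)B the OLE rate.

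- The SAP formula gives (O − B)/B = −r.
- The reduction from the placebo-period rate is q = 1 − (1 − r)/(1 − p).
- The two are linked by r = p + (1 − p)q. On the original baseline, p points precede the drug and (1 − p)q points follow its start.

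**Inputs.** The documents give one pair of figures, the Phase 2a median reductions in Protocol 4.4.4: "in favor of the YKP3089 group, 55% vs 21" percent. I assume, for illustration, that they apply to one subject, so p = 0.21 and r = 0.55.

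- SAP figure: 55% reduction.
- Re-based figure: q = 1 − 0.45/0.79 = 0.43.
- Check: 0.21 + 0.79 × 0.43 = 0.21 + 0.34 = 0.55. So 21 of the 55 points precede the drug (38%) and 34 follow.
- If the placebo-period level simply persisted in OLE (r = p = 0.21), the SAP formula would still show a 21% reduction, and the re-based figure would be 0.

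With r held at 55% and p assumed:

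| Reduction already present on placebo (p) | SAP figure | Reduction from placebo-period rate |
|---|---|---|
| 10% | 55% | 1 − 0.45/0.90 = 50% |
| 21% | 55% | 1 − 0.45/0.79 = 43% |
| 30% | 55% | 1 − 0.45/0.70 = 36% |

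**Regression to the mean alone.** This was simulated with no drug or placebo effect, selecting on the two count criteria only; the 25-day rule was not modelled. The assumptions were a median underlying rate of 5 to 8 per 28 days, between-subject log SD 0.8, within-subject CV 0 to 0.6, and follow-up averaged over six 28-day periods. The median change was about −2% to −15%. A second set of assumptions (median rate 3 to 8, log SD 1.0, gamma-Poisson counts with shape 3 to 12, 18 weeks) gave about −4% to −18%. None of these rates comes from the documents. Regression to the mean is already part of an observed placebo response such as 21%, so the two must not be added.

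**Safety windows.** SAP Appendix 2 has a Start of OLE (Visit 9) row with target Day 127. Its window runs from Day 113 to Day 141 for ECG and laboratory data, and from Day 120 to Day 134 for vital signs. It therefore extends 14 days (141 − 127) or 7 days (134 − 127) past the target, into OLE dosing. No change from this row is planned.

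**The case against.** The case for leaving the plan alone has several parts.

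- *The endpoint is what it says it is.* SAP 11.2.1 labels it as change from the pretreatment baseline, and SAP 11.1 and 11.2.1 exclude inference in OLE. The effect of starting YKP3089 is tested in the randomised comparison. This stands: a reader might infer that an analysis is invalid, and none is.
- *A common baseline keeps the columns comparable.* This stands too. Placebo response and regression to the mean sit in all four groups' figures. A footnote about former placebo subjects alone would wrongly suggest that the other groups' changes are pure drug effect.
- *Not every measure is affected.* Treatment-emergent adverse events start from OLE medication, and examinations and C-SSRS are only listed. A reader might call it inconsistent that adverse events have another reference in the same group. It is not, because treatment emergence needs a treatment start date and SAP 10.1 applies it to all groups.
- *The Visit 9 row already shows safety drift on placebo.* It does so in part. Protocol Table 2 schedules no ECG or laboratory test between Visit 9 and Visit 12 (Day 155), so on-drug values in that row would come from late or unscheduled tests. The row is still not restricted to values before the first OLE dose, and the seizure tables have no counterpart.
- *The re-based contrast is not clean.* Only subjects who completed maintenance and opted in are present (Protocol 6.1), treatment is open-label, and concomitant AEDs may be changed (Protocol 6.1.4.1 and 6.1.4.2). A reader might take the re-based figure as the effect of the drug, and the documents do not support that. It only removes change known to precede the drug.

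One might also infer that the plan throws the within-subject comparison away. That cannot be shown: a separate double-blind SAP and the table templates are not among the documents.

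**Conclusion.** The point holds as a cheap improvement to a descriptive analysis. In this one group the only reference for seizure frequency, laboratory shifts, ECG and vital signs precedes the first YKP3089 dose by 18 weeks. The reported change therefore mixes non-drug change on placebo with whatever follows the start of YKP3089.

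The size in this trial is not in the documents. The illustration (55% reported, 21 of those points before the drug, 43% after re-basing) treats medians from two arms of another study as one subject's values. That study had 12 weeks of treatment and a 200 mg/day target, whereas the OLE runs for years with a 300 mg/day target. A reader might take the 12-point gap between 55% and 43% as the part that precedes the drug. It is not, because the two percentages have different denominators; on these inputs the part that precedes the drug is 21 points. There is no corresponding figure for the safety measures.

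**What to change.** Keep the common baseline for all groups, and make these additions.

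1. *SAP 9 and 11.2.1, former placebo group only:* show each subject's double-blind (placebo) 28-day seizure rate, summarised as for the other rates, and the percent change in OLE rate from it. Count subjects with a zero double-blind rate separately, since their percent change is undefined.
2. *SAP 11.3.2 to 11.3.4, same group:* add the change or shift from the last value before the first OLE dose, selected by dose date and not by the Visit 9 window.
3. *Pooled column:* add a footnote that change from the pretreatment baseline includes non-drug change in all groups and, for former placebo subjects, a period with no YKP3089.
4. *With the re-based figure:* state that completer selection, open-label treatment and permitted AED changes still affect it.

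The double-blind diary and the Visit 9 tests are already scheduled data, and SAP 4 allows revision before the OLE database lock. The cost is a few extra rows for one group, a second reference to explain, and a less favourable figure for that group if its rate fell on placebo.

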10 SAFETY ENDPOINTS

10.1 Adverse Events

For open-label extension analyses, treatment-emergent AEs are defined as AEs with onset after the start of OLE study medication, up to last dose date of OLE study medication + 30 days, or onset before start of OLE study medication and worsened after starting OLE study medication, up to last dose date of OLE study medication + 30 days.

AE relationship to study drug can be classified by the investigator as definite, probable, possible, remote or unrelated. AEs severity can be rated as mild, moderate or severe.

SAEs will be captured from the time of study drug administration in OLE to 30 days after the last dose of study drug, and will be monitored until resolution or stabilization.

10.2 Clinical Laboratory Evaluations

During OLE, laboratory assessments for hematology, serum chemistry, and urine pregnancy test will be performed Visit 9 (start of OLE), Visit 12, 14, 16, every 6 month after Visit 16, and 14 days after the last dose in OLE. Urinalysis will be performed at Visit 9 (start of OLE), Visit 14, 16, every 12 month after Visit 16, and 14 days after the last dose in OLE.

The following laboratory assessments will be performed in this study:

Hematology: hemoglobin, hematocrit, white blood count with differential, RBC count, platelet count, calculated indices.

Serum Chemistry: BUN, calcium, chloride, creatinine, glucose, total bilirubin, direct bilirubin, alkaline phosphatase, AST, ALT, albumin, sodium, potassium, phosphorus and glucose. Serum creatinine will be used to calculate the creatinine clearance.

Urinalysis: pH, specific gravity, protein, glucose, ketone, bilirubin, blood, nitrite, urobilinogen, microscopic examination.

SK LS Protocol YKP3089C017

SAP-OLE Version Final_15May2021 Page 26 of 43 Additional tests: serum pregnancy test.

10.3 Electrocardiograms

ECG parameters consist of heart rate (bpm), PR interval (msec), RR interval (msec), QRS-complex (msec), uncorrected QT interval (msec), and QTcF interval (msec). During OLE, ECG measurements will be performed at Visit 9 (start of OLE), Visit 12, 16, and every 12 months after Visit 16.

10.4 Vital Signs

Vital signs collected in this study are: blood pressure and heart rate (supine for 5 minutes followed by standing for 3 minutes); respiration rate and oral temperature in the supine position. During OLE, these will be collected at Visit 9 (start of OLE), Visits 11, 12, 13, 14, 15, 16, every 3 months after Visit 16, and 14 days after the last dose in OLE.

Weight will only be collected at Visit 9 (start of OLE), Visit 11, 15, 16, every 6 months after Visit 16, and 14 days after the last dose in OLE.

10.5 Physical and Neurologic Examination Results

During OLE, physical examinations will be performed at Visit 9 (start of OLE), Visit 16, and every 12 months after Visit 16.

Full neurological exam will be performed at Visit 9 (start of OLE, at Visit 16, and 14 days after the last dose in OLE. Brief neurological exam will be performed at Visits 11, 13, 15, and every 6 months after Visit 16.

10.6 Columbia Suicide Symptoms and Signs Rating Scale (CSSRS)

C-SSRS Ideation, Intensity and Behavior will be collected at the start of OLE (Visit 9) all visits during OLE: Visit 11, 12, 13, 14, 15, 16, every 3 months after Visit 16, and 14 days after the last dose in OLE.

11 STATISTICAL METHODS

11.1 General Methods

All analyses will be presented by the OLE treatment groups as described in Section 8.1. Categorical variables will be summarized using counts and percentages. Descriptive statistics for continuous variables will include mean, standard deviation, median, minimum, and maximum values. No inferential analysis will be performed for OLE analyses.

SAS® version 9.2 or later will be used for all statistical analyses.

11.2 Efficacy Analysis

11.2.1 Seizure Diary - Percent Change During OLE

The endpoint based on seizure diary is defined as: percent change (reduction) from the pretreatment baseline phase in seizure frequency (average monthly seizure rate per 28 days) of all simple partial motor, complex partial, or secondarily generalized seizures compared with the seizure frequency over the entire OLE phase (overall) and by both 6-month intervals after the start of OLE and cumulative intervals. Endpoint definitions are included in Section 9.

Summary results (mean, SD, median, minimum, and maximum) will be presented by OLE treatment groups for OLE-EA population. Subjects in OLE-EA population with no seizure diary data for the reporting OLE interval will be counted under "missing" category.

There will be no hypothesis testing for efficacy endpoints during OLE. Results will be reported descriptively by OLE treatment groups.

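### The separate 6-month OLE seizure table describes only subjects with diary data in each interval, so its median can improve through response-related drop-out alone

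*SAP*

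**What the plan says.** SAP Section 9 gives the purpose of the OLE diary analysis as to "assess percent reduction in seizure frequency over time in subjects with longer exposure to YKP3089". Three summaries of percent change from the pre-treatment baseline are planned: over the whole OLE, by separate 6-month intervals, and by cumulative intervals that all begin on OLE day 1.

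- **Separate intervals.** The rate is the seizure count in the interval after "dividing by the number of days in the respective 6-month intervals with non-missing seizure data, and then multiplying by 28". No minimum number of diary days is set.
- **Cumulative intervals.** Seizures are counted "during the respective cumulative intervals, dividing by the number of days in the respective cumulative intervals with nonmissing seizure data". Since day 1 is always included, a subject who left early still has data in every later cumulative interval.
- **Population.** OLE-EA (SAP 8.1) takes subjects who "took at least one dose of open-label medication and have any seizure data recorded in OLE seizure diary".
- **No data in an interval.** Under SAP 11.2.1, "Subjects in OLE-EA population with no seizure diary data for the reporting OLE interval" go into a missing category. Mean, SD, median, minimum and maximum are presented, with no hypothesis test.

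Two other places bear on who remains. SAP 8.2 lists lack of efficacy among the recorded reasons for withdrawal. Footnote b to SAP Table 1, like Protocol 6.1.4.2, ties continuation beyond 12 months to benefit from treatment.

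**The concern.** Each row of the separate-interval table is computed on a different set of subjects. Two routes out of the study, withdrawal for lack of efficacy and the 12-month re-evaluation, plausibly depend on response. Later rows may therefore hold a growing share of good responders, and reading down the column would then mix two things: change within subjects and change in who is left. The missing count shows how many have gone, but not how their response differed, so a reader cannot correct the median from it.

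No test is planned, so the displayed medians are the whole result. At stake is whether a later row with a larger reduction is read as an effect that holds or grows. SAP Section 9 defines 20 such intervals to month 120 and one open-ended interval after that, so a small selection per interval has time to accumulate.

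**Working it through.** The plan states no figure for the OLE efficacy analysis, so there is none to reproduce. The check asks how far the interval median can move when no subject's response changes.

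**Inputs (assumed; not in the documents).** Individual percent change is constant over time, normal with mean -50 and SD 35, floored at -100. Poor responders are those with less than a 50% reduction, which is half of the subjects. Drop-out per 6 months is 3% in good responders and 3%, 5% or 10% in poor responders.

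**Formula.** Let S_g and S_p be the fractions of good and poor responders still present. The survivors amount to 0.5 × (S_g + S_p). Their median x lies among the good responders, where F(x) × S_g must equal half of that total. Hence F(x) = 0.25 × (1 + S_p/S_g) and x = -50 + 35 × Φ⁻¹(F).

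**Worked case, 10% vs 3%, months 55–60.** This is the tenth interval, so nine drop-out steps have passed. S_p = 0.90⁹ = 0.387 and S_g = 0.97⁹ = 0.760, a ratio of 0.510. F = 0.25 × 1.510 = 0.377, Φ⁻¹(F) = -0.312, and x = -50 - 10.9 = -60.9. The share still contributing is 0.5 × (0.760 + 0.387) = 57%.

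| Drop-out per 6 months, poor vs good | S_p/S_g after 5 steps | Median, months 31–36 | S_p/S_g after 9 steps | Median, months 55–60 |
|---|---|---|---|---|
| 3% vs 3% | 1.000 | -50.0 | 1.000 | -50.0 |
| 5% vs 3% | 0.901 | -52.2 | 0.829 | -53.8 |
| 10% vs 3% | 0.688 | -56.9 | 0.510 | -60.9 |

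Simulation gives the same values.

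**Second set of assumptions.** Take a median of -55% (the Phase 2a active arm, Protocol 4.4.4), an SD of 40% (Protocol 12.1), and drop-out of 5% to 15% per 6 months in good responders. If poor responders leave at the same hazard, the median stays at about -55%. At twice the hazard it is -58% to -64% in months 19–24 and -62% to -71% in months 43–48. At four times the hazard it is -63% to -73% and -70% to -78%.

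**What the cumulative table would show.** With constant response, each entrant's cumulative value is that subject's own constant response in every row. The median stays flat at -50% (or -55%) whatever the drop-out.

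**When response really changes.** Return to the first model with 10% vs 3% drop-out, and let every subject worsen by 1 point per interval: 9 points by months 55–60.

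| Summary | Months 1–6 | Through or at months 55–60 |
|---|---|---|
| All entrants, if all could be observed | -50 | -41 |
| Separate-interval table | -50 | about -52 |
| Cumulative table (average of each subject's interval values) | -50 | about -47 |
| Fixed cohort with data through 60 months | about -61 | about -52 |

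The interval table shows a slight improvement, the cumulative table shows about 3 of the 9 points, and the fixed cohort shows all 9.

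**Short diaries.** For a subject with baseline 9 and true rate 4.5 per 28 days, the Poisson chance of no seizure in 7 diary days, hence -100%, is exp(-4.5 × 7/28) = 0.32. In 28 days it is exp(-4.5) = 0.01. Such fragments are few. At 10% vs 3%, average drop-out is at most (10% + 3%)/2 = 6.5% per interval. If leaving is spread evenly over 182 days, 6.5% × 28/182 = 1.0% of contributors have under 28 days. Removing 1% of values moves the median by at most half a percentile: 35 × 0.0125 = 0.4 points.

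**The case against.** The strongest reply is that the SAP already plans summaries free of this artefact. The overall and cumulative figures keep every leaver, and a flat cumulative column beside an improving interval column would itself reveal selection. That stands, and it limits the concern to one of three outputs. It is not a full answer, because a cumulative figure averages early and late data and mutes a late change, as the declining-response case shows.

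Second, the stated aim concerns subjects with longer exposure, so describing those who remain is what was intended. That also stands for any single row. It does not cover reading successive rows as a course over time, which the same sentence in Section 9 invites.

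Third, attrition is on view: missing counts by interval (11.2.1), disposition with reasons (8.2) and exposure categories (8.5), with no test whose error rate could suffer. This is correct, and it is why the point is minor.

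Fourth, that later rows hold more good responders is inferred from a withdrawal category and a continuation rule. The documents contain no OLE drop-out rates by response. With equal drop-out the shift is nil, and with 5% vs 3% it is under 4 points at 60 months.

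Finally, a fixed cohort is still selected on staying, and concomitant antiepileptic drugs may be added, removed or adjusted during the OLE (Protocol 6.1.4.2). It therefore shows within-cohort change, not an isolated drug effect.

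**Conclusion.** The point holds for the separate 6-month table only. Its median can improve through response-related drop-out with no change in any subject. In the main illustration the artefact at months 55–60 runs from nil (equal drop-out) through about 4 points (5% vs 3%) to about 11 points (10% vs 3%). These figures rest on assumed drop-out rates and an assumed response distribution. The direction follows from the definitions whenever poor responders leave faster.

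A reader might infer two stronger things. One is that the OLE efficacy analysis as a whole cannot tell a lasting effect from attrition. The documents do not support that: the overall and cumulative summaries retain leavers, and no drop-out data show how strong the selection is. The other is that short diaries drive the apparent trend. They do not: the absence of a minimum number of diary days is a separate, minor matter that mainly touches the minimum and maximum and moves the median by well under 1 point here.

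**What to change.** Add to SAP 11.2.1 a descriptive fixed-cohort version of the 6-month interval table. For example, take subjects with diary data through 12, 24, 36 and 60 months and show each cohort over all its intervals up to that point, with the contributing n in every cell. State that it is to be read beside the cumulative table and that each cohort is selected on remaining in the study.

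A version carrying each leaver's last interval forward is optional. It is a sensitivity display, and it also blurs late change. A minimum number of diary days for an interval rate, such as 28, could be set separately in Section 9 to protect the minimum and maximum. It would drop a few leavers' last fragments.

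The cost is one more descriptive table from data already collected, with no added subject burden. SAP Section 4 allows revision before the OLE database lock; after that, the table can be reported as an additional analysis in the study report.
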